7. RISKS AND DISCOMFORTS

7.1. Blood sampling and intravenous catheter

The risks and discomforts of drawing blood from a vein include the possibility of discomfort, pain, redness, bruising, or bleeding at the site of the blood draw, occasional feeling of lightheadedness, and rarely, infection or fainting.

There are minor risks and discomforts associated with placement of an intravenous line for the PET scan, including the possibility of bleeding, pain, inflammation (redness and swelling), and leaking of contrast agent outside of the vein at the site of the IV. These problems are usually self-limited or require only minor treatments, such as application of an ice-pack or slight pressure for a few minutes.

7.2. Vasodilator stress

Vasodilator-stress with regadenoson and adenosine, as will be performed in this study, has been used routinely for many years for evaluation of known or suspected coronary artery disease in conjunction with myocardial perfusion imaging. During the infusion of the vasodilator stress agent, the patient may experience flushing, chest pain/pressure, nausea, or lightheadedness. If significant symptoms are present, patients will be given aminophylline (reversal agent) IV to relieve these symptoms. There will be continuous monitoring of heart rate, blood pressure, and 12-lead ECG throughout the infusion and recovery. These procedures are routinely performed in patients with CAD, as those in the CIRT trial, and are considered safe.

Regadenoson stress as performed in this study has been used routinely for many years for evaluating patients with known or suspected CAD. The most common side effects associated with the regadenoson bolus include: flushing, chest pain/pressure, shortness of breath, palpitations, headache, mild hypotension and heart block. These side effects are usually mild and self-limiting. If they are severe in intensity, aminophylline IV (1 mg/kg) will be given as per standard protocol.

Subjects with a history of seizures may receive adenosine. The side effects associated with this product include: facial flushing, headache, sweating, palpitations, chest pain, hypotension, shortness of breath/dyspnea, chest pressure, hyperventilation, head pressure, lightheadedness, dizziness, tingling in arms, numbness, apprehension, blurred vision, burning sensation, heaviness in arms, neck and back pain, nausea, metallic taste, tightness in throat, and pressure in groin. Adenosine is administered as a continuous infusion over 4 minutes and administered in a dose of 0.14mg/kg/min. The half-life of adenosine is less than 10 seconds. If the patient is having symptoms the infusion can be stopped, no further medication is administered, and the symptoms would stop within seconds because the medication would already be cleared from the heart. Therefore, no reversal medication is needed.

Rarely, an aminophylline IV injection may be used to reverse side effects of regadenoson infusion. Aminophylline is generally well tolerated; possible side effects of aminophylline may include nausea, headache, restlessness, convulsions, rapid breathing, a rapid heart rate, and allergic reactions such as rash.

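### Section 7.2 directs a reversal drug for significant symptoms under either stress agent, then says none is given after adenosine; the paragraphs must be reconciled

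*Combined protocol and SAP*

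**What the plan says.** Section 7.2 has four paragraphs that bear on this.

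- **Opening paragraph, both agents.** It begins "Vasodilator-stress with regadenoson and adenosine, as will be performed in this study", describes symptoms in general terms ("During the infusion of the vasodilator stress agent, the patient may experience flushing, chest pain/pressure, nausea, or lightheadedness"), and then gives the rule "If significant symptoms are present, patients will be given aminophylline (reversal agent) IV to relieve these symptoms". It makes no exception by agent.
- **Regadenoson paragraph.** After listing common side effects it says "If they are severe in intensity, aminophylline IV (1 mg/kg) will be given as per standard protocol".
- **Adenosine paragraph.** It opens "Subjects with a history of seizures may receive adenosine". On symptoms it says "If the patient is having symptoms the infusion can be stopped, no further medication is administered", explains that the drug clears within seconds, and concludes "Therefore, no reversal medication is needed".
- **Closing paragraph.** It presents aminophylline as a rare measure against the effects of regadenoson, does not mention adenosine, and says that "possible side effects of aminophylline may include nausea, headache, restlessness, convulsions", among others.

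Section 5.4 (Procedures) allows adenosine or regadenoson. It gives no reversal instruction and no rule for choosing between the agents.

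**The concern.** For one event, significant symptoms during an adenosine stress test, the opening paragraph says a reversal drug will be given and the adenosine paragraph says no further drug is given. Staff in the stress laboratory cannot follow both. This is an instruction for an acute safety event in a test that each patient is due to have twice.

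Adenosine is not a marginal agent in this plan. The primary objective in section 2.1 is framed as flow reserve in response to adenosine, and section 5.4 introduces the stress measurement with adenosine before adding regadenoson as an alternative.

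There is a smaller mismatch for regadenoson. The opening paragraph acts on significant symptoms, while the regadenoson paragraph acts on severe ones. A patient whose symptoms are significant but not severe meets the first trigger and not the second.

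**Working it through.** The question is textual. No power, alpha or event-count calculation applies, and the plan gives no figure to reproduce.

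**Step 1. Set the instructions side by side.**

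| Place in 7.2 | Agent covered | Trigger | Action stated |
|---|---|---|---|
| Opening paragraph | Both, by name | Significant symptoms | Aminophylline will be given |
| Second paragraph | Regadenoson | Severe side effects | Aminophylline will be given, with a dose |
| Third paragraph | Adenosine | Symptoms | Infusion can be stopped; no further drug; reversal not needed |
| Closing paragraph | Regadenoson only | Not stated | Aminophylline may be used, rarely |

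**Step 2. Test each combination.**

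- Regadenoson, severe symptoms: the opening and second paragraphs both lead to aminophylline, and the closing paragraph allows it. No conflict.
- Regadenoson, significant but not severe symptoms: the opening paragraph leads to aminophylline; the second paragraph's trigger is not met. The threshold is unclear.
- Adenosine, significant symptoms: the opening paragraph leads to aminophylline; the third says no further drug is given. Direct conflict.

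**Step 3. Look for text that resolves it.** Nothing in 7.2 says that the agent-specific paragraphs prevail over the opening one. Section 5.4 is silent on reversal. The adenosine rate is consistent between the two sections (140 mcg/kg/min in 5.4 is 0.14 mg/kg/min in 7.2, over 4 minutes in both), so the disagreement is confined to the handling of symptoms.

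**Step 4. How often could it arise?** The documents allow only a rough count of all stress tests, both agents together.

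- 30 patients, both scans completed: 30 × 2 = 60.
- If 30 are enrolled and 15% are lost before the second scan (section 6.2 assumes about 15%): 30 + 30 × 0.85 = 30 + 25.5, or about 56.
- If 30 must complete both scans and 15% are lost: 30 / 0.85 = 35.3, so about 36 baseline scans, and 36 + 30 = 66.

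So there would be roughly 56 to 66 tests in all. The conflict concerns only the adenosine tests among them in which significant symptoms occur. Neither the adenosine share nor the expected symptom rate is given, so the count cannot be narrowed.

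**Step 5. Seizure history.** The third paragraph permits adenosine for these patients, and the exclusion criteria in 3.2.2 do not name seizure history, so such patients may be enrolled. The closing paragraph lists convulsions among possible effects of aminophylline. The document does not connect these statements.

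**The case against.** The strongest reply is that the section moves from general to specific. On that reading the opening paragraph is an overview, the later paragraphs set out each agent, and one sentence is simply too broad. The section also sits under Risks and Discomforts and not under Procedures. All scans are done at one experienced laboratory, and the regadenoson paragraph refers to a standard protocol that is not reproduced here. This is a natural reading, and it lowers the chance that practice diverges. But the text does not say that the specific paragraphs prevail, the opening sentence is written as a directive, and 7.2 is the only place that deals with reversal at all. The general-to-specific reading makes the repair easy; it does not remove the need for it.

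Several stronger readings are tempting but unsupported.

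- A reader might infer that any use of a reversal drug breaches one paragraph or another. It does not: aminophylline for severe regadenoson symptoms fits the opening, second and closing paragraphs.
- A reader might infer that the plan directs a drug with a convulsion risk to patients with seizure history. That follows only if the opening paragraph overrides the adenosine paragraph, and it joins statements that the document keeps apart. Adenosine is also only permitted for these patients, and 5.4 does not reserve it for them.
- The absence of a reversal dose for adenosine might look like a further gap. It follows from the adenosine paragraph saying that no reversal is needed.
- The closing paragraph's reference to rare use might look like a third threshold. It can equally be read as expected frequency.

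**Conclusion.** Section 7.2 is internally inconsistent on reversal of stress symptoms. The direct conflict is confined to significant symptoms during adenosine stress; a secondary difference in threshold wording affects regadenoson. The conclusion rests on reading the opening paragraph as covering both agents, which it names, and on the absence of any rule of precedence in 7.2 or 5.4.

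The number of occasions cannot be estimated from the documents. The total of about 60 tests is neither a count of adenosine tests nor a firm ceiling. The seizure and convulsion statements are context for the people who reconcile the text and are not a separate defect.

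This is a wording fault in a participant-safety instruction. It should be corrected, but it does not touch the endpoint, the sample size or the primary analysis.

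**What to change.** Reconcile the paragraphs of 7.2 so that each stress agent has one instruction and one symptom threshold, and make the opening paragraph agree with the agent-specific ones. Keep section 5.4 consistent with the result. In doing so, the investigators should consider patients with a history of seizures, given what 7.2 says about adenosine for them and about the possible effects of aminophylline. The choice of clinical rule is theirs, and none is proposed here.

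The cost is a wording amendment. It adds no patients, visits or procedures and changes no analysis.

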7.3. Radiation risk

The estimated whole body effective radiation dose from each of the ¹³N-ammonia PET scan is ~3-4 mSv⁵⁵, comparable to the annual radiation dose from background radiation sources in North America. Each subject will undergo 2 PET studies during the trial for a total dose of ~6-7 mSv, significantly lower than the average radiation exposure associated with a single conventional myocardial perfusion imaging study using single-photon emission computed tomography (SPECT)⁵⁵.

7.4. Drug side effects and toxicities

The most common side effects with the use of B/F/TAF are nausea, diarrhea, and headache, as described in Table 3 which is based on the results of the phase III trials^{49, 50}.

Table 3. Drug side effects

	B/F/TAF group (n=314)	DTF/ABC/3TC group (n=315)
Any adverse event (AE)	265 (84%)	283 (90%)
Grade 3 or 4 AE	19 (7%)	25 (8%)
Drug-related AE	82 (26%)	127 (40%)
Drug-related serious AE	0	4 (<1%)
Any AE leading to study drug discontinuation	0	4 (1%)*
AE occurring with ≥5% incidence in either group		
Nausea	32 (10%)	72 (23%)
Diarrhea	40 (13%)	41 (13%)
Headache	36 (11%)	43 (14%)
Upper respiratory tract infection	20 (6%)	34 (11%)
Nasopharyngitis	23 (7%)	29 (9%)
Fatigue	19 (6%)	27 (9%)
Syphilis	12 (4%)	25 (8%)

Insomnia	14 (4%)	20 (6%)
Arthralgia	11 (4%)	19 (6%)
Vomiting	12 (4%)	17 (5%)
Cough	20 (4%)	8 (3%)
Bronchitis	10 (3%)	16 (5%)
Abdominal pain	9 (3%)	16 (5%)

Data are in n (%). B/F/TAF=bictegravir, emtricitabine, and tenofovir alafenamide. DTG/ABC/3TC= dolutegravir, abacavir, and lamiduvine. *Chronic pancreatitis and steatorrhea (n=1), nausea and generalized rash (n=1), depression (n=1), and thrombocytopenia (n=1).^{49, 50}

7.5. Reproductive risks

Pregnant or breastfeeding patients will be excluded from this study.

A female is considered of child-bearing potential unless:

- Permanently sterile (includes hysterectomy, bilateral oophorectomy, or bilateral salpingectomy)
- Medically documented ovarian failure
- Post-menopausal, defined as ≥ 60 years of age with cessation of menses for ≥ 12 months.

7.6. Unknown Risks:

There may be other risks and side effects that are not known at this time.

8. POTENTIAL BENEFITS

8.1. Potential benefits to participating individuals

There are no direct benefits for the patient from taking part in this study. The proposed study will test the important question of whether reducing endothelial cell activation and dysfunction using B/F/TAF will quantitatively improve coronary flow reserve, a sensitive measure of myocardial ischemia. Thus, this pilot study will provide important and unique mechanistic insights of the capabilities of novel HIV therapies to improve key determinants of clinical risk (improve coronary blood flow and reduce ischemia) and, in so doing, improve patient symptoms and quality of life, as well as outcomes.

8.2. Potential benefits to society

Data collected in this pilot trial may provide important mechanistic insights into presumed cardiovascular benefits from novel HIV therapies, as well as into the pathophysiology of microvascular dysfunction in HIV-AIDS.

9. MONITORING AND QUALITY ASSURANCE

9.1. Safety monitoring

The PI of the study will monitor the overall safety of the study and will report any adverse events to the IRB, per local institutional guidelines. The PI will also monitor this study to ensure that subjects' human rights, safety, and well-being are protected, that the study is properly conducted in adherence to the current protocol, and study data reported by the investigator/subinvestigator are accurate, complete and verifiable with study-related records such as source documents.

Safety data will be obtained at each study visit from the spontaneous reports by patients of adverse events, vital sign monitoring, physical examinations, 12-lead ECGs and clinical laboratory tests. In addition, telephone follow-up will be conducted to assess for any adverse events. All safety data will be reviewed by an HIV physician investigator ([name]).

Patients with unexpected abnormalities on the baseline PET scan will be discussed with the patient's PCP/ID physician to decide whether the patient should participate in this pilot trial. The findings will be discussed with the patient and the patient's primary physician in order to facilitate an appropriate management plan. If a patient is excluded on safety grounds, we do not think that this will affect our ability to determine the effect of B/F/TAF on myocardial blood flow.

The safety of B/F/TAF will be assessed with respect to the following end points: (1) death from any cause, (2) the composite of death from any cause or any cardiovascular hospitalization, (3) frequency of symptomatic documented arrhythmia, (4) serious adverse events related to the study drug and clinically significant laboratory abnormalities.

9.2. Treatment Compliance

Subject compliance to treatment regimen will be assessed at each study visit by a count of remaining medication in each bottle. Subjects will be asked to complete a medication diary for additional compliance assessment. The diary will be compared to the drug count. A threshold of $\geq 80\%$ will be used to define compliance with treatment assignment. Subjects determined to be noncompliant ($< 80\%$ compliance) will be counseled regarding the importance of following dosing instructions but not withdrawn from the study.

9.3. Discontinuation criteria for individual subjects

Discontinued subjects are those who are enrolled in the study and for whom study treatment is terminated prematurely for any reason. The subject is free to withdraw from the study treatment and/or study for any reason and at any time without giving reason for doing so and without penalty or prejudice. The investigator is also free to terminate a subject's involvement in the study at any time if the subject's clinical condition warrants it.

Subjects will be discontinued if:

- Subject experiences a serious or intolerable adverse event
- Subject has severe disease and has to be intervened upon based on the imaging tests
- In the Investigator's opinion, the subject is non-compliant with the protocol requirements
- Subject's health would be jeopardized by continued participation
- Subject wishes to withdraw consent
- Investigator elects to end the study

9.4. Adverse event reporting guidelines

9.4.1 Definition of Adverse Events (AEs)

An adverse event (AE) is defined as any untoward medical occurrence in a subject administered a study drug, and which does not necessarily have a causal relationship with this treatment. An AE can therefore be any unfavorable and unintended sign (including an abnormal laboratory finding),

symptom, or disease temporally associated with the use of a study drug, whether or not related to the study drug.

An abnormality identified during a medical test (e.g., laboratory parameter, vital sign, ECG data, physical exam) should be defined as an AE only if the abnormality meets one or more of the following criteria:

- Induces clinical signs or symptoms
- Requires active intervention
- Requires interruption or discontinuation of study medication
- The abnormality or investigational value is clinically significant in the opinion of the investigator

9.4.2 Definition of Serious Adverse Events (SAEs)

A serious AE is any untoward medical occurrence that, at any dose:

- Results in death,
- Is life threatening (an event in which the subject is at risk of death at the time of the event; it does not refer to an event which hypothetically might have caused death if it was more severe),
- Results in persistent or significant disability/incapacity,
- Results in congenital anomaly, or birth defect,
- Requires inpatient hospitalization or leads to prolongation of hospitalization (hospitalization for treatment/observation/examination caused by AE is to be considered as serious)
- Other medically important events

Medical and scientific judgment should be exercised in deciding whether expedited reporting is appropriate in other situations, such as important medical events that may not be immediately life-threatening or result in death or hospitalization but may jeopardize the subject or may require intervention to prevent one of the other outcomes listed in the definition above. These events, including those that may result in disability, should also usually be considered serious.

9.4.3 Criteria for Causal Relationship to the Study Drug

Adverse events that fall under either "Possible" or "Probable" should be defined as "adverse events whose relationship to the study drugs could not be ruled out."

Causal relationship to the study drug	Criteria for causal relationship
Not Related	A clinical event, including laboratory test abnormality, with a temporal relationship to drug administration which makes a causal relationship improbable, and/or in which other drugs, chemicals or underlying disease provide plausible explanations.
Possible	A clinical event, including laboratory test abnormality, with a reasonable time sequence to administration of the drug, but which

	could also be explained by concurrent disease or other drugs or chemicals. Information on drug withdrawal may be lacking or unclear.
Probable	A clinical event, including laboratory test abnormality, with a reasonable time sequence to administration of the drug, unlikely to be attributed to concurrent disease or other drugs or chemicals, and which follows a clinically reasonable response on re-administration (re-challenge) or withdrawal (de-challenge).

9.4.4 Criteria for Defining the Severity of an Adverse Event

The following standard with 3 grades is to be used to measure the severity of adverse events, including abnormal clinical laboratory values.

- Mild: No disruption of normal daily activities
- Moderate: Affect normal daily activities
- Severe: Inability to perform daily activities

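### Section 9.4.4 grades laboratory adverse events only by effect on daily activities, so a symptom-free one is recorded as Mild however extreme the value

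*Combined protocol and SAP*

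**What the plan says.** Section 9.4.4 gives a single scale and states that it covers laboratory results: "The following standard with 3 grades is to be used to measure the severity of adverse events, including abnormal clinical laboratory values". The grades are "Mild: No disruption of normal daily activities", "Moderate: Affect normal daily activities" and "Severe: Inability to perform daily activities". None of them refers to a laboratory value, a multiple of a reference limit or a change from an earlier value.

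Section 9.4.1 decides which test results are graded at all: "An abnormality identified during a medical test (e.g., laboratory parameter, vital sign, ECG data, physical exam) should be defined as an AE only if" at least one of four criteria is met. The first is that it causes signs or symptoms. The other three need none: "Requires active intervention", "Requires interruption or discontinuation of study medication", or the investigator's opinion that the finding is clinically significant.

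Section 9.1 lists four safety end points, the last being "serious adverse events related to the study drug and clinically significant laboratory abnormalities". Section 5.5 schedules a metabolic panel, blood count and HIV RNA at screening, Day 45 and End of Treatment. Section 6.4 describes the CFR test and the biomarker associations, and gives no analysis of adverse events or safety laboratory data.

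**The concern.** A severity grade is meant to rank events by intensity. For symptoms, the effect on daily life is a reasonable measure. For a laboratory value it is not, because a patient can feel well with a markedly abnormal result. Section 9.4.4 nonetheless requires that measure for laboratory values. This is an explicit rule applied to data that it cannot rank, and not merely a missing detail.

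At stake is how the trial's laboratory safety is described. If adverse events are tabulated by the only severity measure the protocol prescribes, symptom-free laboratory events will tend to fall in the lowest category. A reader of that table could take this as evidence that laboratory changes after the switch were small, when the grade carries no information on their size.

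**Working it through.** No arithmetic applies, because the document gives no figure that depends on the grade. The check sets the sections side by side.

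1. **Which laboratory findings are graded?** Under 9.4.1, only those that meet at least one of the four criteria. A change that meets none is not an adverse event and receives no grade.

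2. **Can a symptom-free finding be an adverse event?** Yes, by three of the four criteria: intervention, interruption or discontinuation of study drug, or clinical significance in the investigator's opinion.

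3. **What grade does it receive?** Under 9.4.4, Moderate and Severe both need an effect on daily activities. If there is none, only Mild remains, at any value. If an investigator held that treating the abnormality itself disrupted daily life, the grade would reflect the burden of treatment and still not the value.

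4. **Can the grade separate small from extreme?** Take two symptom-free patients. One has a result slightly out of range that is judged clinically significant. The other has a far more extreme result that leads to interruption of study drug. Both events are Mild. The order can even reverse: a modest change that produces symptoms affecting daily activities is graded Moderate, above the extreme symptom-free one.

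5. **Does another section supply laboratory grading or a summary?** None supplies a numeric grading. Section 6.3 lists change in inflammatory and cardiac biomarkers as a secondary end point, but this does not cover the metabolic panel, blood count or HIV RNA. Section 6.4 plans no summary of those.

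6. **What else depends on the grade?**

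| Item | Section | Basis | Uses the severity grade? |
|---|---|---|---|
| Laboratory safety end point | 9.1 | Clinical significance | No |
| Serious adverse event definition and reporting | 9.4.2, 9.4.5 | Seriousness | No |
| Discontinuation of a subject | 9.3 | Serious or intolerable event, jeopardised health, other listed reasons | No |
| Follow-up of adverse events | 9.4.6 | All adverse events | No |
| Primary analysis | 6.4 | Paired t-test on CFR | No |
| Sample size of 30 | 6.2 | CFR assumptions | No |

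Steps 1 to 5 establish the defect. Step 6 limits its reach to the recorded severity of laboratory adverse events.

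**The case against.** The strongest defence is that no listed decision turns on the grade. A dangerous symptom-free result would still be recorded, followed up and, where medically important, reported as serious. Section 9.1 also has an HIV physician investigator review all safety data. This stands, and it is why the point is minor. It does not correct the grade: the same event could be recorded as both serious and Mild.

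It may also be said that investigators would use judgement. Section 9.4.4 prescribes the scale and offers no laboratory alternative, and with four recruiting sites informal departures could differ between sites.

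A reader might infer three stronger claims that the document does not support:

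- **That every symptom-free laboratory change is Mild.** Section 9.4.1 excludes from grading any change that meets none of its criteria.
- **That the trial cannot show the severity of laboratory changes at all.** The section 9.1 end point rests on clinical significance and not on the grade, and the values collected under section 5.5 would allow the size of changes to be reported. What is missing is a commitment to report it.
- **That Table 3 gives the size of the problem or a comparator.** Its Grade 3 or 4 row counts adverse events of all kinds, with no laboratory subset. The phase 3 trial of the two regimens described in section 5.2 enrolled treatment-naive adults, whereas this trial switches virologically suppressed patients. Section 7.4 uses the table to describe side effects, and no section plans a comparison with it.

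**Conclusion.** The concern holds in a limited form. As written, section 9.4.4 grades a symptom-free laboratory adverse event as Mild whatever the value, so the prescribed severity grade cannot separate small from extreme laboratory adverse events. No planned summary of safety laboratory values makes up for this.

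Severity is minor. The defect affects the description of laboratory safety and nothing in the CFR analysis, the sample size, the section 9.1 end point or the reporting of serious events. The number of events affected cannot be worked out from the document; it could be zero or more.

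The conclusion assumes that sites apply 9.4.4 as worded and that no laboratory grading table exists in a document outside the one reviewed.

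**What to change.** In section 9.4.4, restrict the daily-activities scale to clinical signs and symptoms. State that laboratory values are graded on a named, published numeric toxicity table of the sponsor's choice.

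In section 6.4, add a short descriptive summary: for each laboratory parameter that the table covers, the number of patients by worst post-switch grade, together with the change from the most recent pre-switch value and the date of that value.

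The date matters. Section 5.1 accepts non-pregnancy laboratory results from up to one year around the screening visit, and the baseline list in section 5.5 contains only hs-troponin and NT-proBNP. The pre-switch metabolic panel, blood count or HIV RNA may therefore be old, and the summary should make this visible.

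The cost is one paragraph of protocol text and one small table. Grading uses values already collected, so no new samples are needed.
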